# 3 Study Design

This study is a non-randomized, observational, phase IV, multi-site pilot study to investigate the compliance with and perceptions of treatment, as well as HRQOL in surgically resected melanoma patients undergoing HDI or PEG IFN therapy. After discussion with their treating physician, patients will receive 1 of 2 approved adjuvant therapies for melanoma:

- 1. Cohort A: high-dose interferon alfa (HDI, Intron® A)
- 2. Cohort B: pegylated alfa-interferon 2b (PEG IFN, SylatronTM)

Although the study is not randomized, in order to attempt to discern a difference between the groups, a maximum of a 60:40 split will be allowed on the protocol. This means that a

maximum of 60% of patients will be permitted on either arm and if achieved, that particular arm will be capped at 60%.

Each treatment arm will have a pretreatment phase (within 4 weeks/28 days of starting the induction phase (4 weeks of HDI or 8 weeks of PEG IFN), a maintenance phase (treatment administration at specified times up to 1 year), and an end-of-study assessment, conducted within 21 days of discontinuation of study treatment.

The primary endpoint of this study is to compare compliance with treatment of HDI and PEG IFN. Patients will complete drug administration diaries to track compliance with the recommended dosing schedule. Secondary endpoints include comparing treatment perceptions and HRQOL between treatment groups, comparing the frequency of Grade 3 and Grade 4 adverse events (AEs) in each treatment arm, and evaluating the reasons for patients' choice of treatment with HDI or PEG IFN through the use of the Interferon Preference Questionnaire

Patients receiving HDI will complete the CCSQ and FACT-BRM at baseline, every 2 weeks during the induction phase and monthly during the maintenance phase (beginning at Day 29) for up to 1 year. Patients receiving PEG IFN will complete the CCSQ and FACT-BRM at baseline, 2 weeks, 4 weeks, 6 weeks, and monthly during the maintenance phase (beginning at Day 57) for up to 1 year. Adverse events will be monitored throughout the study. Any dose adjustments based on toxicities will be made according to investigator judgment and the package insert for each product. Patients will also be queried to determine the most important reasons for choice of treatment with HDI versus PEG IFN.

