#### 6 Visit Schedule and Assessments

Table 2 and Table 3 are suggested assessments for both treatment arms and suggested visit procedures are indicated with an "x." This study schedule is a suggested guideline and can be modified per institutional standard practice guidelines, with the exception of QoL, which is mandatory at the time points as indicated.

Table 2: Schedule of Events Cohort A: HDI Suggested schedule of events (QOL evaluation is mandatory)

Test/Assessment	Pretreatment a	D1	D8 b	D15 b	D22 b	Maintenance Phase c
Informed consent	X					
Medical history	X					
Interferon preference questionnaire	X					
ECOG PS	X					
Weight/vital signs d		X	X	X	X	X
Physical examination e		X				X
Hematology labs f		X	X	X	X	X
Chemistry labs g		X	X	X	X	X
Collection and Monitoring of		X	X	X	X	X
Grade 3 and 4 AE and all SAEs h						
QoL evaluations i		X		X		X
Drug administration diary j		X	X	X	X	X

Treatment: Induction Phase: Suggested dosing per package insert is 20 million IU/m² IV infusion over 20 minutes, 5 consecutive days per week for 4 weeks; Maintenance Phase: 10 million IU/m² SC injection 3 times per week for 48 weeks. Dosing can be modified per institutional guidelines.

- a Within 4 weeks (28 days) of starting HDI
- b For Days 8, 15, and 22, if HDI was delayed, the study assessment schedule for these dates will also be delayed
- c . Maintenance dose begins at day 29 and then monthly until last dose of HDI.
- d Weight should be obtained at baseline. Vital signs should be performed at each visit.
- e Physical examination should be performed monthly or according to institutional protocol.
- Hematology labs will be done as clinically indicated and will include hemoglobin, hematocrit, RBC count, WBC count, platelets, as well as total and differential neutrophil counts. Hematology labs should be performed weekly during the induction phase or according to institutional protocol.

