Treatment: Induction Phase: Suggested dosing per package insert is 6 mcg/kg/week SC for 8 doses (8 weeks); Maintenance Phase: 3 mck/kg/week SC injection for up to 5 years (this study will only evaluate the first year of treatment). Dosing can be modified per institutional guidelines.

- a Within 4 weeks (28 days) of starting PEG IFN
- b For Days 8, 15, 22, 29, 36, 43, and 50 if PEG IFN was delayed, the study assessment schedule for these dates will also be delayed
- Maintenance dose begins at day 29 and then monthly until last dose of PEG IFN, or until treatment discontinuation or one year of therapy
- d Weight should be obtained at baseline. Vital signs should be performed at each visit.
- e Physical examination should be performed monthly or according to institutional protocol.
- Hematology labs will be done as clinically indicated and will include hemoglobin, hematocrit, RBC count, WBC count, platelets, as well as total and differential neutrophil counts.. Hematology labs should be performed weekly during the induction phase or according to institutional protocol.
- g Chemistry labs will be done as clinically indicated and should include albumin, creatinine kinase (CPK), or urea blood urea nitrogen (BUN), creatinine, alanine aminotransferase (ALT), aspartate aminotransferase (AST), lactate dehydrogenase (LDH), serum alkaline phosphatase, direct and total bilirubin, glucose, total protein, sodium, potassium, chloride, bicarbonate (HCO3) (CO2; venous blood), calcium, and phosphorous. Chemistries should be performed weekly during the induction phase or according to institutional protocol. Specific individual chemistry labs may be omitted according to investigator judgment if not included in the institution's chemistry profile.
- h All Grade 3 and 4 adverse events (regardless of whether they occur on treatment or non-treatment weeks) will be collected until the last day of treatment and submitted utilizing the corresponding AE forms. Additionally, all SAEs, regardless of grade will also be collected.
- Treatment perceptions and HRQOL data will be collected via CCSQ and FACT-BRM, respectively, at baseline, 2 weeks, 4 weeks, 6 weeks, and monthly during the maintenance phase (beginning at Day 57) for up to 1 year. These questionnaires are to be completed prior to the administration of the dose for that visit. If dose is held or changed, QoL is still to be completed.

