#### 6.4 Weight and Vital Signs

Weight and vital signs (temperature, pulse rate and blood pressure) should be recorded at baseline. Vital signs should be obtained weekly during induction and monthly during maintenance or according to institutional protocol.

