#### 7.1 **Adverse Events**

An adverse event is the appearance or worsening of any undesirable sign, symptom, or medical condition occurring after starting the treatment even if the event is not considered to be related to the treatment. Treatment includes the investigational drug under evaluation and the comparator drug or placebo that is given during any phase of the study. Medical conditions/diseases present before starting treatment are only considered AEs if they worsen after starting treatment. Abnormal laboratory values or test results constitute AEs only if they induce clinical signs or symptoms, are considered clinically significant, or require therapy.

The occurrence of AEs should be sought by non-directive questioning of the patient at each visit during the study. Adverse events also may be detected when they are volunteered by the patient during or between visits or through physical examination, laboratory test, or other assessments. All Grade 3 or 4 AEs and all SAEs regardless of grade, must be recorded on the AE CRF with the following information:

- 1. the severity grade (3 or 4 AEs and all SAEs regardless of grade)
- 2. its relationship to HDI or PEG IFN therapy (suspected/not suspected)
- 3. its duration (start and end dates or if continuing at final exam)

All adverse events should be treated appropriately. Treatment may include one or more of the following: no action taken (ie, further observation only); treatment dosage adjusted/temporarily interrupted; treatment permanently discontinued due to this adverse event; concomitant medication given; non-drug therapy given; patient hospitalized/patient's hospitalization prolonged. The action taken to treat the adverse event should be recorded on the AE CRF.

Once an adverse event is detected, it should be followed until its resolution or until it is judged to be permanent, and assessment should be made at each visit (or more frequently, if necessary) of any changes in severity, the suspected relationship to the treatment, the interventions required to treat it, and the outcome.

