Item CS13, which rates the chemotherapy regimen overall, will be presented descriptively for the two treatment groups at the end of the study (i.e., 12 months). No inferential analyses will be conducted for this item.

- To evaluate the treatment-related side effects that may impact the patient's health-related QoL (HRQOL) using the Functional Assessment of Cancer Therapy of Biologic Response Modifier (FACT-BRM), with a 30% between-group difference in scores deemed clinically relevant, a mixed randomized-repeated measures ANOVA will be conducted for all items as a summation score, similar to the analysis plan described for CCSQ items CS1 GP5 (page 23, second bullet point). Separate subscales will be presented descriptively for the two treatment groups.
- The frequency of Grade 3 and 4 toxicities, according to the National Cancer Institute (NCI) Common Toxicity Criteria for Adverse Events (CTCAE) for patients on standard HDI versus PEG IFN, will be presented descriptively for the two treatment groups at 2 weeks, 3 months, 6 months and 12 months. No inferential analyses will be conducted for this outcome.
- Patients' reasons for their choice of treatment with HDI versus PEG IFN, for those cases in which patients are presented with a choice of either treatment option, will be reported descriptively at the study's conclusion (i.e., 12 months). No inferential analyses will be conducted for this outcome.

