- Treatment-related side effects that may impact the patient's health-related QoL (HRQOL) using the Functional Assessment of Cancer Therapy of Biologic Response Modifier (FACT BRM), with a 30% between-group difference in scores deemed clinically relevant. Time points of comparison were baseline/week 1, week 3, week 13, week 25, and week 50.

- The frequency of Grade 3 and 4 adverse events (AEs), according to the National Cancer Institute (NCI) Common Toxicity Criteria for Adverse Events (CTCAE) for patients on standard HDI versus PEG IFN, and the frequency of severe adverse events (SAEs), regardless of grade.
- Patients' reasons for their choice of treatment with HDI versus PEG IFN at the study's conclusion, for those cases in which patients were presented with a choice of either treatment option.

All analyses were conducted using IBM SPSS Statistics for Windows, Version 25.0 (Armonk, NY: IBM Corp.), with $p < .05$ denoting statistical significance.

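### If the suggested schedule is followed, PEG IFN has four scheduled checks to HDI's one in weeks 5 to 8, and the Grade 3/4 comparison neither aligns nor reports this difference

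*Protocol*

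**What the plan says.** Comparing Grade 3 and 4 AE frequency between arms is a named secondary endpoint (Protocol Synopsis and Section 3). Five elements of the plan decide how often such events are looked for.

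- **Laboratory tests.** The footnotes to Tables 2 and 3 give one rule for both arms: "Hematology labs should be performed weekly during the induction phase or according to institutional protocol". Chemistry follows the same rule.
- **Vital signs.** Section 6.4: "Vital signs should be obtained weekly during induction and monthly during maintenance or according to institutional protocol".
- **Phase length.** Section 3 has "induction phase (4 weeks of HDI or 8 weeks of PEG IFN".
- **Calendar.** For HDI, the Table 2 footnote reads "Maintenance dose begins at day 29 and then monthly until last dose of HDI". For PEG IFN, the Table 3 footnote on delays lists weekly assessment days: "For Days 8, 15, 22, 29, 36, 43, and 50 if PEG IFN was delayed". Two other Table 3 footnotes disagree on when PEG IFN maintenance starts. The maintenance footnote says Day 29; the questionnaire footnote says Day 57, as Section 3 does.
- **AE enquiry.** Section 7.1: "The occurrence of AEs should be sought by non-directive questioning of the patient at each visit during the study".

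For analysis, Protocol Section 9 says that Grade 3 and 4 toxicity "will be presented descriptively for the two treatment groups at 2 weeks, 3 months, 6 months and 12 months", with no inferential test. The SAP lists "The frequency of Grade 3 and 4 adverse events (AEs), according to the National Cancer Institute (NCI) Common Toxicity Criteria" and gives no time points. Neither document aligns the check schedules or reports the number of checks per arm.

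**The concern.** An abnormality that comes and goes between checks is recorded only if a check falls inside it or someone reports it. Under a phase-based schedule, HDI moves to monthly checks at Day 29, while PEG IFN on an 8-week induction stays weekly until Day 57. Even with identical true event rates in weeks 5 to 8, more short events could be found on PEG IFN. Within each arm, the detected rate can also fall when monthly checks begin, and a reader could take that for improving tolerability.

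The protocol saw the unequal inductions when it chose time points for the repeated-measures analyses, and says so there. It does nothing comparable for AEs. The comparison is descriptive, but a detection difference does not need a test to mislead, and the pilot is meant to inform whether a larger trial is warranted.

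**Working it through.** The documents give no check-frequency figure to reproduce, so the counts come from the schedule text, taking a month as 28 days (assumption).

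**1. Scheduled check days**

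- HDI: Days 1, 8, 15, 22, then 29, 57, 85 and every 28 days.
- PEG IFN, 8-week induction: Days 1, 8, 15, 22, 29, 36, 43, 50, then 57, 85 and every 28 days.
- PEG IFN, if monthly checks begin at Day 29: the same days as HDI.

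| Window | HDI | PEG IFN, 8-week induction | PEG IFN, monthly from Day 29 |
|---|---|---|---|
| Weeks 1–4 (Days 1–28) | 4 | 4 | 4 |
| Weeks 5–8 (Days 29–56) | 1 | 4 | 1 |
| First 91 days | 7 | 10 | 7 |
| Through Day 364 | 16 | 19 | 16 |

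**2. Detection inside weeks 5–8.** Assume an abnormality starts on a random day from 29 to 56, lasts L days and is visible only at a check. On PEG IFN with weekly checks it is always found for L of 7 or more. On HDI the relevant checks are Days 29 and 57. For L = 7, start days 29 and 51–56 qualify, so 7/28 = 25%. For L = 14 it is 14/28 = 50%, and for L = 21 it is 21/28 = 75%.

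**3. Effect on a cumulative summary.** Assume equal and constant true rates in both arms and no discontinuation. Let H be weeks of follow-up, w the weeks with weekly checks (4 on HDI, 8 on PEG IFN), d the event duration in weeks (d ≥ 1) and s the share of events that only a check can reveal.

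- Detectable weeks: D = w + (H − w) × min(1, d/4)
- With share s: s × D + (1 − s) × H
- H = 13, d = 1, s = 1: HDI 4 + 9 × 0.25 = 6.25; PEG IFN 8 + 5 × 0.25 = 9.25; ratio 1.48
- H = 52, d = 1, s = 1: HDI 4 + 48 × 0.25 = 16; PEG IFN 8 + 44 × 0.25 = 19; ratio 1.19
- H = 13, d = 1, s = 0.25: HDI 0.25 × 6.25 + 0.75 × 13 = 11.31; PEG IFN 0.25 × 9.25 + 0.75 × 13 = 12.06; ratio 1.07
- H = 52, d = 1, s = 0.25: HDI 0.25 × 16 + 0.75 × 52 = 43; PEG IFN 0.25 × 19 + 0.75 × 52 = 43.75; ratio 1.02

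| PEG IFN/HDI ratio | 1 week, all need a check | 2 weeks, all need a check | 1 week, a quarter need a check | 4 weeks or more |
|---|---|---|---|---|
| 13 weeks | 1.48 | 1.24 | 1.07 | 1.00 |
| 26 weeks | 1.32 | 1.13 | 1.03 | 1.00 |
| 52 weeks | 1.19 | 1.07 | 1.02 | 1.00 |

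The protocol does not say whether its time points are cumulative. If the 3-month summary covered only weeks 3–13, the extreme case would be (6 + 5 × 0.25)/(2 + 9 × 0.25) = 7.25/4.25 = 1.71, and later intervals would be at 1.00.

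**4. Contact in the other direction.** HDI induction is 5 infusion days a week for 4 weeks, so 20 contacts in weeks 1–4, against 4 weekly PEG IFN doses. The step 1 counts leave these out.

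**The case against.** A reader might infer that PEG IFN patients are in fact checked four times as often and that the Grade 3/4 comparison is therefore tilted against PEG IFN. The documents do not support that, for four reasons.

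- **The schedule is only suggested.** Section 6 lets sites modify everything except the questionnaires, and laboratory tests are done as clinically indicated. Actual checks per arm are unknown. This stands, so the count is conditional. The mandatory questionnaires are themselves uneven, though: within Days 29–56, HDI has Day 29, while PEG IFN has weeks 4 and 6.
- **Table 3 contradicts itself.** If monthly checks on PEG IFN began at Day 29, weeks 5–8 would be 1 against 1 and the difference would vanish. This stands too. It is not for this review to say which start is right.
- **HDI's 20 infusion days could raise detection on HDI in weeks 1–4.** This stands, and it leaves the net direction open. It falls in a different window, so it does not cancel the weeks 5–8 difference in a way anyone can verify; a pooled frequency hides both.
- **Many events do not depend on checks.** Section 7.1 counts events volunteered between visits, and diaries capture AE onset. An abnormal laboratory value is an AE only if it is symptomatic, clinically significant or treated. This limits the size. It does not remove the issue, because a value judged clinically significant can qualify on laboratory evidence alone, and Section 9.2 summarises laboratory data separately.

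Equal true rates are also an assumption of convenience: in weeks 5–8 of an 8-week induction, PEG IFN is at its induction dose and HDI at its maintenance dose. An excess on PEG IFN in that window could be real toxicity.

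**Conclusion.** The point holds in conditional form. If the suggested schedule is followed with an 8-week PEG IFN induction, scheduled checks in weeks 5–8 are 4 on PEG IFN to 1 on HDI. That can inflate detected short-lived, mainly laboratory, Grade 3/4 events on PEG IFN in any summary covering those weeks, and the plan offers no means of seeing it.

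The size is modest outside that window. The 3-month summary is the most exposed. The SAP's single frequency is closest to the one-year figures, between 1.00 and about 1.2. Early discontinuation would shorten follow-up and move the ratio towards the shorter-horizon values. All these ratios rest on equal, constant true rates, 28-day months and adherence to the suggested days; they illustrate a range and do not estimate a bias. A net tilt against PEG IFN over the whole study is possible but not shown.

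**What to change.** 1. Reconcile the Day 29 and Day 57 statements for PEG IFN in Table 3, and report which calendar sites followed.
2. Keep all Grade 3/4 AEs in the main comparison.
3. Add a table of Grade 3/4 AEs by weeks 1–4, 5–8 and 9 onward, using AE start dates. Beside each window, give the actual number of visits and laboratory draws per arm. The weeks 5–8 row is where any detection effect will concentrate, so it should not be read without those counts.
4. Add a sensitivity summary of laboratory results and laboratory-type AEs limited to the check days both arms share: Days 1, 8, 15, 22, 29, 57 and every 28 days after. State a rule for matching delayed visits to these days. Identify laboratory-type AEs by MedDRA term, because mode of detection is not among the AE CRF items listed in Section 7.1.
5. State that a fall in event rate after induction will not be interpreted as improving tolerability.

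The cost is SAP wording and some extra tabulation, with no change to visits. Start and end dates are already required on the AE CRF; visit and draw dates may have to come from source documents. The SAP is written as if the data were in hand, so the added tables should be labelled post hoc. The shared-day summary leaves out some genuine PEG IFN events and should be supportive only.

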#### 6.1 Patient Demographics/Baseline Characteristics

Patient demographic and baseline characteristic data will be collected for all patients enrolled in the study, including relevant medical history.

#### 6.2 Interferon Preference

For situations in which the investigator offered both treatment options, patients will be queried regarding their reasons for the choice of either HDI or PEG IFN using a standardized questionnaire created for this study (see Appendix 13.3).

#### 6.3 ECOG Performance Scale

The Eastern Cooperative Oncology Group Performance Scale (ECOG PS) assesses the patients' general well-being and activities of daily life (see Appendix 13.4).

#### 6.4 Weight and Vital Signs

Weight and vital signs (temperature, pulse rate and blood pressure) should be recorded at baseline. Vital signs should be obtained weekly during induction and monthly during maintenance or according to institutional protocol.

## 6.5 Physical Examination

A complete physical examination will be performed at baseline and monthly for the duration of the study or according to institutional protocol. The physical examination should include examination of general appearance, skin, neck (including thyroid), eyes, ears, nose, throat, lungs, heart, abdomen, back, lymph nodes, extremities, vascular, and neurological.

Information for all physical examinations must be included in the source documentation at the study site. Significant findings made after the start of treatment that meet the definition of a Grade 3 or Grade 4 adverse event must be recorded on the AE CRF.

## 6.6 Clinical Laboratory Evaluations

Clinical laboratory assessments will be performed by local laboratories as clinically indicated. Routine laboratory tests (hematology and clinical chemistry) should be performed at the time points designated in the schedule of events for both treatment cohorts (Table 2 and Table 3).

# 6.7 Treatment Perceptions and Health-Related Quality of Life Assessments

The CCSQ will be used to ascertain patients' perceptions of their chemotherapy regimen in terms of its convenience and their overall level of satisfaction. Treatment-related side effects

that may impact the patient's HRQOLwill be evaluated using the FACT-BRM. Patients will complete these mandatory assessments at the time points specified in Table 2 and Table 3.

#### 6.7.1 CCSQ

The CCSQ is a questionnaire for oncology patients used to evaluate their overall satisfaction with and preferences for chemotherapy. The CCSQ was generated from interviews with 70 oncology patients, 7 oncologists, 4 nurses, and focus groups of 14 nurses. Interviews took place in the US, the United Kingdom, and France and were qualitatively analyzed. The CCSQ was designed for adults with a wide range of cancer types and stages and contains 21 items and 7 domains:

- 1. Expectations of chemotherapy
- 2. Feelings about side effects
- 3. Oral chemotherapy compliance
- 4. Convenience
- 5. Satisfaction with chemotherapy
- 6. Stopping chemotherapy
- 7. Reasons for non-compliance

#### 6.7.2 FACT-BRM

The FACT-BRM is a questionnaire designed to evaluate HRQOLin cancer patients who are receiving treatment with biologic response modifiers. The FACT-BRM contains 6 domains:

- 1. Physical well-being
- 2. Social/family well-being
- 3. Emotional well-being
- 4. Functional well-being
- 5. Additional concerns Physical
- 6. Additional concerns Mental

